#### Data Analysis:

Aim 1: We will employ linear mixed effects models to examine within- and between-group variability in positive stimulant urine drug screens across 6 weeks.

Aim 2: We will employ linear mixed effects models to examine within- and between-group differences in (H2) client and therapist WAI ratings and (H5) attendance rates.

Aim 3: We will use linear mixed effects models to assess within- and between-group differences in the following stress measures related to the Trier Social Stress Test (conducted at baseline and post-6 weeks): (H3) Psychophysiological measures (HR, HRV), (H4) self-reported stimulant craving, (H6) salivary stress biomarkers (cortisol and DHEA), and (H7) self-reported anxiety (STAI-6).

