STIMULANT OXYTOCIN STUDY

NCT03016598

[figure not shown]
12/18/2017

Study Protocol

RESEARCH DESIGN

We conducted a randomized, double-blind, placebo-controlled study to examine the effects of oxytocin administration on stimulant use, psychosocial treatment engagement, and stress-reactivity in a sample of 40 individuals with stimulant use disorder receiving opioid agonist therapy within an opioid treatment program at the San Francisco and Oakland VA. Following successful screening and an initial baseline visit, participants were randomized to receive either oxytocin 40 IU or placebo intranasally twice daily for six weeks.

FIGURE 1

Research Participants:

We enrolled 40 male research participants with active stimulant use disorder and stabilized on opioid agonist therapy in an opioid treatment program (OTP). OTP clinics operate under strict state and federal guidelines for treatment structure and monitoring. Each patient receiving opioid agonist therapy from the OTP who is actively using stimulants is in “Phase 0” within the OTPs at the San Francisco and Oakland VA. Phase 0 patients must report to the clinic every day the clinic is open for observed opioid agonist dosing (i.e., no take-home doses), must submit urine for random toxicology screening approximately once every two weeks, and are required to attend weekly psychoeducation/therapy groups within the clinic. All patients in the OTP are assigned an individual counselor who meets with them at least monthly to support the lifestyle changes necessary to progress in recovery. Phase 0 patients typically meet with their counselors more frequently.

Recruitment: Participants were recruited from the OTP through the use of flyers posted visibly in clinic common areas and referrals from clinic counselors who were made familiar with inclusion/exclusion criteria through presentations at staff meetings and “Dear Provider” letters.

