Adherence Monitoring: Study staff trained in proper spray application (Guastella, Hickie, et al. 2013) intranasally administered participants’ morning study drug doses. Each participant was given a nasal spray bottle and trained in proper spray application by study staff. Participants were to administer their evening dose 8-10 hours following their morning dose. Each week, participants will be incentivized to bring their nasal spray bottle from the previous week, whether full or empty, for adherence monitoring via weighing. We successfully used similar contingent management strategies in our previous study of

repeated oxytocin administration in patients with co-occurring cocaine and opioid use disorders. Our participants brought their nasal spray devices in for weighing 98% of the time (no participant forgot more than once) and collectively self-administered >78% of their evening doses.

Randomization: Participants were randomized 1:1 to receive either oxytocin or placebo. A randomization plan was created using www.randomization.com. Randomization was managed by the Investigational Drug Pharmacist at the San Francisco VA, who also managed the double blind.

Inclusion Criteria: Participants must be at least 18 years old, enrolled as a patient at the San Francisco or Oakland VA OTP, be on a stable dose of methadone or buprenorphine for at least two consecutive weeks, and have at least one documented routine urine toxicology screen positive for cocaine or methamphetamine in the past month.

Exclusion Criteria: Urine toxicology screen positive for heroin in the past month; meeting *Diagnostic and Statistical Manual of Mental Disorders, 5th Edition* (DSM-V) criteria for previous or current psychotic disorder, severe neuropsychological disorder, premenstrual dysphoric disorder, or current moderate severe alcohol use disorder; active suicidal or homicidal ideation; hemodialysis; sensitivity to E 216, E 218, and chlorbutanol hemihydrate (preservatives used in nasal spray); using hormone supplementation; positive urine pregnancy test or women of child-bearing age not practicing an effective means of non-hormonal birth control; or nasal obstruction, discharge, or bleeding.

METHODS

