All measures are listed in detail below. In sum, our primary outcome measure will be **(1)** Stimulant positive urine drug screen collected at baseline and weekly throughout the study. To assess psychosocial measures, participants and their clinic assigned counselor will complete **(2a)** the Working Alliance Inventory – Short Revised (WAI-SR) (Hatcher & Gillaspy 2006), client and therapist forms, respectively, at baseline and after six weeks as well as **(2b)** OTP attendance rates. Additionally, in response to a Trier Social Stress Test, we will measure, **(3a)** self-reported stimulant craving by completing the Cocaine Craving Questionnaire (CCQ-Brief) modified to include methamphetamine in addition to cocaine, **(3b)** psychophysiological measures, including heart rate and heart rate variability, **(3c)** stress biomarker measurements, including salivary cortisol and DHEA, and **(3d)** self-reported anxiety.

See **Figure 1** for Study Design Outline.

PROCEDURES

Screening/Baseline: Potential participants were screened by study staff on site and, if preliminarily eligible, signed a brief clinic-specific consent in order for us to confirm eligibility via OTP medical records. Eligible participants were invited for a baseline interview, which included: 1) written informed consent, 2) a medical history and brief physical exam conducted by a study physician, 3) a structured mental health interview conducted by an advanced psychology trainee, 4) baseline measurements, and 5) a urine pregnancy test (for female participants).

Daily: We asked participants to report daily on their illicit drug use from the previous 24-hours, including specific drug, amount, and route of administration. We also monitored daily OTP clinic attendance.

Weekly: Participants provide a weekly urine sample, which was analyzed for various drugs of abuse.

MEASURES

[figure not shown]
Screening Measures:

- 1) **Structured Clinical Interview for DSM-5 Disorders – Clinical Trials Version (SCID-5-CT):** a structured psychiatric interview based on current diagnostic standards, customized to the inclusion and exclusion criteria of our clinical trial.

Outcome Measures:

- 1) **Stimulant positive urine drug screen:** (Jufer, Wstadik et al. 2000, Preston, Epstein et al. 2002) was measured from baseline and weekly urine samples. Urine samples were screened for a variety of drugs of abuse.

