- 2) a. **Working Alliance Inventory – Short Revised (WAI-SR):** (Hatcher & Gillaspy, 2006): is a well-validated 12-item measure of therapeutic alliance. Participants completed individual “client forms” for their clinic-assigned individual counselor at baseline and after six weeks. Likewise, the counselor completed the “therapist form” for each participant at baseline and after six weeks of study participation. Time required for administration per form: <5 minutes.
b. **Attendance in OTP clinic:** Daily attendance at OTP clinic was tracked for each participant.

FIGURE 2

Psychophysiology measurements
Baseline CCQ-Brief, salivary biomarkers, Likert scales
Figure 6: Social Stress-Induced Cocaine Craving Paradigm. TSST = Trier Social Stress Test, CCQ-Brief –Cocaine Craving Questionnaire-Brief, salivary biomarkers = cortisol and dehydroepiandrosterone, Likert scales = subjective stress and anxiety.

- 3) **Trier Social Stress Test (TSST) (see Figure 2):** in order to evaluate response to social stress, participants engaged in the TSST paradigm at study baseline and after six weeks of intranasal oxytocin or placebo. The TSST is a standardized and well-validated psychological stress challenge which has shown utility for evoking a strong cardiovascular and HPA axis stress response (including salivary cortisol) in a laboratory setting (Dickerson & Kemeny 2004). After a 5-minute preparation period, participants are instructed to give a speech and perform serial subtractions, for five minutes each, in front of a panel of stone-faced adjudicators.
 - a. **Cocaine Craving Questionnaire-Brief (CCQ-Brief):** (Sussner, Smelson et al. 2006) is a valid and reliable 10-item self-report instrument, with each item scored on a scale 1-7, used to measure the respondent's general cocaine craving. We amended this to also include methamphetamine and asked for participants' stimulant of choice. Participants

completed the amended CCQ-Brief at baseline, immediately after the TSST, and 20 minutes after the TSST.

- b. **Psychophysiological Stress Measures:** consisted of two main outcome variables: *heart rate* and *heart rate variability*. We recorded continuous physiology during the TSST, we will include the 5-min averages for: baseline, speech prep, speech, mental arithmetic, and 15-20 mins post-TSST.

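### Does the Aim 1 mixed model need a stated rule for missed weekly urine screens?

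*SAP*

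**What the plan says.** The opening of the protocol's Methods section names the primary outcome: "Stimulant positive urine drug screen collected at baseline and weekly throughout the study". The SAP's Data Analysis section gives Aim 1 one sentence: "We will employ linear mixed effects models to examine within- and between-group variability in positive stimulant urine drug screens across 6 weeks". The available text states no missing-data assumption, no rule for a missed or refused sample, no imputation and no sensitivity analysis. Part of the SAP was not available, so the absence can be asserted only for the text at hand.

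Four other places bear on the point.

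- Research Design: the trial is run "in a sample of 40 individuals with stimulant use disorder", allocated 1:1 and treated for six weeks.
- Procedures (Daily) and Outcome Measures 2b: auxiliary data exist. "We asked participants to report daily on their illicit drug use from the previous 24-hours, including specific drug, amount, and route of administration", and "Daily attendance at OTP clinic was tracked for each participant". Aim 1 gives neither a role.
- SAP Aim 2: attendance is a hypothesised outcome, through "within- and between-group differences in (H2) client and therapist WAI ratings and (H5) attendance rates".
- Research Participants and Adherence Monitoring: clinic patients who are still using stimulants are due in person on each day the clinic is open for observed dosing, and study staff gave the morning study dose. The only compliance figure comes from a previous study, for bottle return: "Our participants brought their nasal spray devices in for weighing 98% of the time".

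**The concern.** A person who has just used stimulants has a reason not to give urine, so missed samples may be positive more often than those provided. A mixed model fitted to the available screens keeps participants with gaps, but it relies on the missed results being predictable from the observed ones. If that fails, and fails differently in the two arms, the arm difference is biased. Oxytocin is hypothesised to change attendance, so it is natural to fear that the two arms lose samples for different reasons.

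The primary comparison is also small: 40 / 2 = 20 participants per arm, at most 20 × 6 = 120 post-baseline screens per arm and 240 in all. A bias of several percentage points could matter, and the text available would not tell a reader whether the result survives it.

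**Working it through.** The plan gives no power, positivity, dropout or missed-sample figure, so there is nothing of its own to reproduce. Only the 20 per arm and six weekly screens come from the documents; every rate below is an assumption.

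**1. Raw proportions.** Let p be the true positive rate. If positives are missed with probability a and negatives with probability b, the observed rate is p(1 − a) / [p(1 − a) + (1 − p)(1 − b)]. Take p = 0.70 in both arms, with a flat 10% missed in the comparison arm, whose observed rate stays at 0.70.

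- a = 0.30, b = 0.10: 0.49 / (0.49 + 0.27) = 0.645, a false difference of −5.5 points.
- a = 0.50, b = 0.10: 0.35 / (0.35 + 0.27) = 0.565, or −13.5 points.
- a = 0.05, b = 0.02, with 2% missed in the comparison arm: 0.665 / (0.665 + 0.294) = 0.693, or −0.7 points. This takes the 98% bottle-return figure as a rough guide.

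**2. The mixed model itself.** A simulation used 20 per arm, six screens, no true effect and a random-intercept linear mixed model with an arm effect, 1,200 runs per setting. At p = 0.70 and within-person correlation 0.1 / 0.3 / 0.5 / 0.7, the bias was:

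- 30% of positives missed in one arm, 10% otherwise: −5.3 / −4.3 / −3.3 / −1.9 points;
- 50% of positives missed in one arm, 10% otherwise: −12.9 / −10.9 / −8.1 / −5.2 points;
- 30% against 10% missed, unrelated to the result: between −0.06 and −0.01 points, with rejection of 4.2–5.6%;
- 5% of positives in one arm, 2% otherwise: −0.6 to −0.2 points.

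Over 60–80% positivity the standard error was about 7 to 14 points. Rejection at the 5% level was about 4–10% in the 30% case and 5–36% in the 50% case.

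**3. A second model form.** Here the random intercept was on the logit scale (SD 1.5), positivity was about 60%, and the model adjusted for week and baseline result; 3,000 runs, no true effect. Each x/y is the percentage missed when the governing result is negative/positive.

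| Missingness | Mean difference (points) | Rejection |
|---|---|---|
| 15% completely at random, both arms | 0.1 | 5.2% |
| Last observed result, oxytocin 5/30; placebo flat 20 | 0.1 | 5.6% |
| Last observed result, oxytocin 5/45; placebo flat 10 | 0.1 | 6.0% |
| Current result, 5/25 in both arms | −0.3 | 6.1% |
| Current result, oxytocin 5/30; placebo 5/10 | −4.9 | 9.0% |
| Current result, oxytocin 5/30; placebo flat 20 | −5.9 | 11.3% |
| Current result, oxytocin 5/45; placebo flat 10 | −10.8 | 21.9% |

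Rows 2 and 3 matter most. Missingness that differs strongly by arm but follows the last observed result leaves the model essentially unbiased. Material bias appears only when the unseen current result drives missingness differently by arm.

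**4. Same pattern in both arms.** This is harmless only when there is no true effect. With true rates of 60% and 80% and 30%/10% of positives/negatives missed in both arms, the observed rates are 0.42 / 0.78 = 53.8% and 0.56 / 0.74 = 75.7%. The difference is 21.8 points instead of 20.

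**5. Would a fixed rule do better?** Counting every missed screen as positive, with 30% against 10% missed for reasons unrelated to the result, creates a false difference of (0.30 − 0.10)(1 − p): 8, 6 and 4 points at p = 0.6, 0.7 and 0.8. In the setting of row 3 it gives +6.1 points and 12.1% rejection, where the available-data model is unbiased. Applied to both arms it does not bound the arm difference either, since that needs opposite assignments by arm. Imputation from self-report (assumed sensitivity 0.7–0.9, specificity 0.9, a report available for every missed sample) still leaves 2.1 to 3.7 of the 5.5 points.

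**The case for a change.** The strongest case for amending the plan runs as follows. The omission is real and affects the primary outcome. The population and the attendance hypothesis make result-dependent missingness credible. The documented incentive is for returning bottles, with none stated for urine. Daily reports and attendance are already collected, so sensitivity analyses would be cheap, and without a prior statement the handling could be chosen after the results are seen.

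The omission and the conditional bias stand. The rest is weaker.

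- An effect on attendance implies unequal missing rates, which step 2 shows to be harmless when unrelated to the result. Nothing in the documents indicates result-dependence that differs by arm.
- Daily in-person dosing gives repeated chances to collect a weekly sample. It does not prove that few were missed, but it makes losses of 30–50% of positives in one arm hard to presume.
- The bias depends on a contrast that the plan leaves open. An arm-by-week slope over weeks 1 to 6 under the 30% pattern gave about zero (−0.1 and +0.1 points, Monte Carlo error 0.3). Adding a complete baseline brought it back to between −2.4 and −11.4 points, with standard errors of 12–18.
- Routine clinic screens may not be usable to fill gaps, since record access is described only "in order for us to confirm eligibility via OTP medical records".
- Much of the protocol is in the past tense, so an addition might not count as pre-specification.

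**Conclusion.** No change to the plan follows. This is missing detail that analysts fill sensibly: a likelihood-based mixed model on all available screens is the usual choice, and it is approximately unbiased under missing at random, even when missing rates differ by arm. Stating that assumption, tabulating missed samples by arm and week, and showing how far the result depends on them are ordinary reporting steps. None would alter the primary estimate, and the obvious replacement rule can be worse.

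The size of any bias cannot be fixed from the documents, nor can its direction. Under assumed rates it runs from 0.2–0.6 points, if samples were missed about as rarely as bottles were in the previous study, through 1.9–5.3 points in the 30% case at 70% positivity, to 14.1 points at the extreme tried (50% of positives missed in one arm, 60% positivity, correlation 0.1). The conclusion rests on a likelihood-based fit to all available screens and on the absence of any evidence in the documents that missingness depends on the unseen result differently by arm. It would need revisiting if the missed-sample table showed heavy losses concentrated in one arm.

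### Aim 1 fits a linear mixed model, by default with one constant residual variance, to a yes/no urine screen; if positivity changes materially, its standard errors for change, within-arm and trend contrasts can be miscalibrated

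*SAP*

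**What the plan says.** The Protocol (Methods) defines the primary outcome as "Stimulant positive urine drug screen collected at baseline and weekly throughout the study". Over six weeks that is up to seven positive/negative results per participant.

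The SAP (Data Analysis, Aim 1) gives the analysis in one sentence: "We will employ linear mixed effects models to examine within- and between-group variability in positive stimulant urine drug screens across 6 weeks". Aims 2 and 3 name the same class of model for alliance ratings, attendance, heart rate, craving, salivary markers and anxiety. The Aim 1 sentence gives no link function, visit-specific variance or robust standard error. It also names no contrast, random-effects structure or role for the baseline screen.

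On size and population, the Protocol states "We enrolled 40 male research participants with active stimulant use disorder" and "Participants were randomized 1:1 to receive either oxytocin or placebo", so about 20 per arm. To enter, a participant must "have at least one documented routine urine toxicology screen positive for cocaine or methamphetamine in the past month". No expected or observed baseline positive rate is given.

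**The concern.** A linear mixed model in its default form gives every observation the same residual variance. A binary result cannot have that property when its mean changes: the variance is largest at 50% positive and shrinks towards 0% or 100%. People who are almost always positive also have little room to change, so change on the percentage scale varies between people even when the two arms behave alike.

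The estimated difference in percent positive is not the problem. What suffers is the standard error, and with it the interval and p-value for the primary outcome of a 40-person trial. Depending on the pattern of positivity and the contrast, the test can be too cautious, which loses power, or too liberal, which produces false positives. Aim 1 promises results within and between arms over the weeks, so change and trend contrasts are within its scope.

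**Working it through.** The text gives no power calculation or expected rate for Aim 1, so there is no planned figure to reproduce. The check compares the standard error the model would report with the true one.

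**Inputs from the documents.** 40 participants, 1:1, so 20 per arm; baseline plus six weekly binary results.

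**Assumptions.** Complete data; two-sided 5% test; random-intercept linear model with a mean for each arm and week; baseline modelled as an outcome; each participant's log-odds of a positive screen shifted by a normal effect with SD 1.5 to 2.5. The positive rates are assumed.

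**Step 1: variance of one result, p(1-p).** 95%: 0.0475. 90%: 0.09. 80%: 0.16. 60%: 0.24. 50%: 0.25. From 95% to 60% this is a five-fold change (0.24/0.0475 = 5.05).

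**Step 2: one case by formula.** Both arms 95% at baseline, then 75%, SD 1.5. Numerical integration over the participant effect gives a covariance of 0.01555 between baseline and any week, and 0.04904 between any two weeks. The variances are 0.0475 (baseline) and 0.75 x 0.25 = 0.1875 (each week).
- Sum of variances: 0.0475 + 6 x 0.1875 = 1.1725.
- Sum of all 49 entries of the covariance matrix: 1.1725 + 12 x 0.01555 + 30 x 0.04904 = 2.8303.
- Common residual variance in the model: (1.1725 - 2.8303/7)/6 = 0.1280.
- Model variance of (weeks 1-6 mean minus baseline), per participant: 0.1280 x (1 + 1/6) = 0.1494.
- True variance: 0.0475 + (0.1875 + 5 x 0.04904)/6 - 2 x 0.01555 = 0.0885.
- Standard error of the arm difference, sqrt(2 x variance/20): model 0.122, true 0.094. Ratio 1.30.
- Approximate type I error, 2[1 - Phi(1.96 x 1.30)]: 1.1%.

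**Step 3: the same formula elsewhere, no treatment effect (ratio = model SE / true SE).**

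| Both arms | Contrast between arms | SD 1.5 | SD 2.0 | SD 2.5 |
|---|---|---|---|---|
| 95%, then 75% | weeks 1-6 mean minus baseline | 1.30 | 1.20 | 1.11 |
| 90%, then 75% | same | 1.19 | 1.15 | 1.11 |
| 80%, then 75% | same | 1.05 | 1.04 | 1.04 |
| 75% throughout | same | 1.00 | 1.00 | 1.00 |
| 95% falling to 60% | slope over weeks | 0.93 | 0.88 | 0.83 |
| 95% falling to 60% | week 6 minus baseline | 0.99 | 0.96 | 0.93 |

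**Step 4: simulated type I error (nominal 5%).** Repeated simulations gave 1.1-3.6% for the weeks 1-6 mean minus baseline after a 90-95% baseline, and 6.5-11% for the slope when both arms fall from 95% to 60%. With a milder fall, 85% to 65%, the slope test rejected in 5.0-6.7%. A test using participant-level errors stayed within 4.3-5.8%.

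**Step 5: within-arm contrasts.** Here the correlation was modelled differently (Gaussian copula, latent correlation 0.3 or 0.6). With placebo flat at 95% and oxytocin falling from 95% to 50%, the slope ratio is about 1.5 within placebo and 0.70-0.79 within oxytocin.

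**Step 6: power.** For 50% vs 75% positive after a 90% baseline, using the weeks 1-6 mean minus baseline, power is 47% with the model's errors against 60% with valid ones (SD 1.5), and 57-58% against 60% (SD 2.5).

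**Step 7: where nothing goes wrong.** For a single comparison of 90% vs 60%, the true SE is sqrt(0.09/20 + 0.24/20) = 0.128. Using the average variance 0.165 in both arms gives sqrt(2 x 0.165/20) = 0.128, the same. A comparison of weeks 1-6 means alone had type I error of 4.6-5.2%.

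**The case against.** The strongest reply is that the defect appears only after choices the SAP does not state, and much of that reply stands.

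- **Random effects.** A reader might infer that the miscalibration is independent of the random-effects structure. It is not: the inflated slope error comes from a random-intercept-only model, which the SAP does not specify. One set of simulations that added a random slope, for the 95% to 60% fall, gave 3.3-4.5% (t, 38 df) or 4.1-5.1% (normal reference). That result has not been repeated, and 63-88% of those fits were on the covariance boundary, so a random slope may remove the inflation but is not an assured cure.
- **Baseline.** The over-wide case needs baseline in the model as an outcome. Aim 1 refers only to the six weeks, whereas Aim 3 names baseline explicitly. If baseline is a covariate or is left out, that half goes.
- **Ceiling.** It is tempting to read the entry rule as placing baseline near 100%. It requires one positive in the past month, and the Protocol puts routine screens about two weeks apart. Someone positive half the time would qualify with probability 1 - 0.5 x 0.5 = 75%, taking two independent screens. A 75-80% baseline is as compatible with the documents as 90-95%, and nothing in them supports a 35-point fall in both arms.
- **Unseen text.** The SAP uses labels H2 to H7 without defining them in Data Analysis. The contrast may be stated in text not available here.
- **Linear scale.** A linear model is a reasonable way to estimate a difference in percent positive. That stands, and the fix keeps it.

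What survives is that the stated method is linear, its default variance does not suit the outcome, and the Aim 1 sentence contains nothing to correct it. If a logistic mixed model was meant, the SAP should say so.

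**Conclusion.** The concern holds conditionally. The mechanism is certain, but its size depends on rates, a contrast and a random-effects structure that the documents do not give. Under the assumptions above, standard errors run from about 1.3 times too wide (change from a 90-95% baseline) to about 17% too narrow (slope, random intercept only). Type I error then lies between about 1% and 11%, and up to 13 points of power (60 - 47) are lost in the case tried. Within-arm contrasts can be further off.

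The documents do not support a flat statement that the primary p-value or interval is wrong. With flat rates, a baseline near 75-80% followed by little change, or a comparison of weeks 1-6 means alone, the default model is close to right. The change is still worth making, because the rates cannot be known when the analysis is fixed and the participant-level error held its level in every scenario tried.

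**What to change.** In Aim 1:
1. State that the weekly screen is analysed as a binary outcome, and name the primary contrast, the role of the baseline screen and the random-effects structure.
2. Report the arm difference in percent positive with standard error, interval and p-value from a participant-level robust variance with small-sample correction: CR2 with Satterthwaite degrees of freedom, or a two-sample t test on each participant's own contrast.
3. As a sensitivity analysis, fit a binomial-logit model to weeks 1-6 (GEE with bias-corrected errors, or a logistic mixed model). Do not enter baseline as an outcome in that model: an arm that is 100% positive at baseline breaks the fit. At a 90% baseline the chance of this in at least one arm of 20 is 1 - (1 - 0.9^20)^2 = 23%, in line with 100-129 unusable fits per 500 simulated trials.

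The cost is SAP wording and a few lines of code, with no new data. The downside is that intervals widen wherever the linear model's were too narrow.

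### The available Aim 1 text does not say how the baseline urine screen enters the model; entering it as a covariate costs almost nothing and protects against chance imbalance in that screen

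*SAP*

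**What the plan says.** The SAP (Data Analysis, Aim 1) proposes linear mixed effects models for "within- and between-group variability in positive stimulant urine drug screens across 6 weeks". The available analysis text mentions baseline only for the Aim 3 stress-test measures.

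The Protocol (METHODS) defines the primary outcome as "Stimulant positive urine drug screen collected at baseline and weekly throughout the study". Under Outcome Measures it repeats that the screen "was measured from baseline and weekly urine samples". The data for a baseline term therefore exist.

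On size and allocation the Protocol says "We enrolled 40 male research participants with active stimulant use disorder" and "Participants were randomized 1:1 to receive either oxytocin or placebo", which gives about 20 per arm. The Randomization paragraph names no stratification factor. To enter, a participant must "have at least one documented routine urine toxicology screen positive for cocaine or methamphetamine in the past month". Patients of the type enrolled "must submit urine for random toxicology screening approximately once every two weeks".

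One SAP section that precedes Data Analysis was not available, and it may state the role of baseline.

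**The concern.** The same measurement could play three parts in this model: a covariate, a time-zero outcome row, or none. These are different analyses of the primary outcome, and the available sentence fits any of them.

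The choice matters only if baseline screens vary. Entry needs one positive routine screen in a month that holds about two, so the study's own baseline screen can be negative for some participants. Nothing in the Randomization paragraph limits chance imbalance between two small arms. If the arms differ at baseline and the screen is not used, the weeks 1-6 estimate tends to move towards that imbalance, and some precision is given up.

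**Working it through.** There is no plan figure to reproduce on this point: the available text gives no alpha, power, effect size, positive-screen rate or within-person correlation.

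**Inputs from the documents.** 40 participants, 1:1, one baseline and six weekly screens, entry on at least one recent positive screen.

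**Inputs assumed.** Positive rates, between-person variation (logit SD 1, 1.5, 2, 3), individual trend SD (0, 1, 2), mean logit (0, 1, 2), one or two pre-entry screens, and 15% of weekly screens missing at random.

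**Step 1: chance imbalance.** With baseline positive share p, the SD of the difference between arms is sqrt(2p(1-p)/20).
- p = 0.56: sqrt(2 x 0.56 x 0.44/20) = 0.157. The exact binomial probability of a difference of 20 points or more (4 or more participants of 20) is 26.5%.
- p = 0.87: sqrt(2 x 0.87 x 0.13/20) = 0.106. The probability is 9.7%.

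The simulation below produced baseline shares of 0.56-0.87 and a probability of 9.6-27.2%.

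**Step 2: how adjustment works.** Let D_Y be the arm difference in mean weeks 1-6 positivity, D_B the arm difference in baseline positivity, and b the pooled within-arm slope of the outcome on the baseline screen. The adjusted estimate is D_Y - b x D_B. In a simpler complete-data simulation at p = 0.7 and SD 2, D_Y moves 0.37 per unit of D_B. A 20-point imbalance therefore shifts it 0.37 x 0.20 = 0.074, or 7.4 points. After adjustment the shift is -0.005 x 0.20 = -0.001. The correlation of baseline screen with outcome is 0.54, so the expected variance ratio is about 1 - 0.54^2 = 0.71; the simulated ratio is 0.72.

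**Step 3: simulation with no drug effect.** Random-intercept linear mixed model on weeks 1-6, entry rule imposed, 72 settings of 5,000 trials. Ranges are across settings.

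| Quantity | Baseline not used | Baseline as covariate |
|---|---|---|
| Rejection, all trials | 4.4-5.8% | 4.4-5.7% |
| Mean shift towards the imbalance, trials with a baseline difference of 20 points or more | 1.5 to 8.9 points | -1.0 to 0.9 points |
| Rejection in those trials | 5.4-14.3% (median 8.4%) | 3.0-6.4% (median 4.8%) |

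The variance cut from adjustment, by between-person SD, is -1 to 5% (SD 1), 6-12% (1.5), 9-19% (2) and 17-27% (3), with a median of 10.5% over all settings. If every baseline screen is positive, the covariate is constant and there is no gain.

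**Step 4: what the precision is worth.** For an assumed log-odds effect of -1.5 from week 1 (mean logit 1, trend SD 1), power at SD 1/1.5/2/3 is 88/73/58/41% without the screen and 88/77/64/50% with it.

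**Step 5: what is not removed.** A single yes/no screen measures underlying use with error. In the complete-data simulation (shares 0.50-0.95, SD 1-3), the correlation between the estimate and the arm difference in underlying use falls only from 0.42-0.87 to 0.39-0.63.

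**Step 6: baseline as time zero in a slope.** Over weeks 0-6 the mean time is 3 and the sum of squared deviations is 9+4+1+0+1+4+9 = 28. Suppose baseline differs by D_B and each later week by beta x D_B. The slope difference then shifts by (-3 + 3 x beta) x D_B/28, which is negative whenever beta is below 1. With beta = 0.37 and D_B = 0.20 this is -3 x 0.63 x 0.20/28 = -0.0135 per week, or -0.081 (8.1 points) over six weeks, in the direction opposite to the imbalance. In simulated null trials with a baseline difference of 20 points or more, this slope was falsely significant in about 9-14%.

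**The case against.** The strongest reply is that the plan may already use the screen. The primary outcome is defined to include baseline, and a model of change within and between groups can naturally be read as group by time with baseline as week zero. The unavailable SAP section may say so. This stands to the extent that the documents show the role of baseline to be unstated, not that it is left out. It does not settle the matter, because a weeks 0-6 slope lacks the protection of a covariate (Step 6). A model that holds both arms to a common baseline mean was not evaluated here.

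A second reply is that the gain is modest and may be nil, because entry on a recent positive screen may leave most participants positive at baseline. This also stands, and it limits how strongly the change can be urged.

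Three stronger readings are tempting and not supported:
- A reader might infer that omitting baseline biases the trial or inflates its overall error rate. Randomisation prevents average bias, and both models reject about 5% over all null trials.
- A reader might infer that adjustment removes baseline imbalance altogether. It deals with the observed screen only (Step 5).
- A reader might infer that the plan lacks a deciding comparison or relies on within-group change. The unavailable section may name the comparison, and neither matter is part of this point.

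**Conclusion.** The point holds as a gap in specification with a nearly free improvement attached, not as an error that invalidates Aim 1. The available text leaves the baseline screen's role open. Covariate adjustment removes, on average, the shift due to chance imbalance in that screen. In the roughly 10-27% of null trials with a baseline difference of 20 points or more, it brings false positives from about 5-14% down to 3-6%. The precision gain depends almost entirely on how much participants differ from one another: negligible at logit SD 1 and about a quarter of the variance at best at SD 3. Confidence is medium, because every rate, SD, trend and missingness figure is assumed and part of the SAP was not seen.

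**What to change.** First check the SAP section that precedes Data Analysis. If it already gives the baseline screen a role, confirm which one.

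If it does not, add one sentence to Aim 1: in the oxytocin-versus-placebo comparison, the weeks 1-6 screens are the outcome and the baseline screen (positive/negative) is a fixed covariate. State that the same screen is not also entered as a time-zero outcome row. Do not treat a weeks 0-6 group-by-time slope as equivalent.

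The change needs no new data or visits. It uses one degree of freedom (40 - 3 = 37 between participants, against 40 - 2 = 38) and can lose about 1% of variance if participants differ little. The Protocol describes enrolment and randomisation in the past tense, so the change must be dated before unblinding or labelled post hoc.
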